## 6.3 Exclusion Criteria

Patients who meet any of the following exclusion criteria will be excluded from the study:

- Has received 1 or more dose(s) of a potentially effective systemic antibacterial treatment
  within the 72 hours prior to the first dose of test article (a subject will be considered to have
  received a potentially effective systemic antibacterial treatment if the pathogen identified as
  causing infection is shown to be susceptible to the antibacterial given or, in the circumstance
  where a pathogen is not identified, if the antibacterial agent is approved for treatment of
  pneumonia or is known to have activity against any of the leading causes of CABP [eg, *Streptococcus pneumoniae, Haemophilus influenzae, Moraxella catarrhalis, Staphylococcus
  aureus, Legionella pneumophila*]). EXCEPTION: Subjects (not exceeding 25% of the total
  study population) may be eligible despite prior antibacterial therapy if they have been treated
  with a single dose of a short-acting antibacterial (ie, an antibacterial whose standard dosing
  regimen is more frequent than once per day, see list in Appendix 4).
- 2. Is known or suspected to have CABP caused by a pathogen that may be resistant to either test article (eg, *Pseudomonas aeruginosa*, *Proteus* spp., *Morganella morganii*, *Providencia* spp., *Pneumocystis jiroveci*, obligate anaerobes, mycobacteria, fungal pathogens).
- 3. Suspected or confirmed empyema (a parapneumonic pleural effusion is not an exclusion criteria) or lung abscess.
- 4. Confirmed or suspected severe acute respiratory syndrome coronavirus 2 (SARS-CoV-2) infection based on local standard-of-care assessments available during Screening.
- 5. Subjects who reside in a long-term care or subacute/intermediate healthcare facility (eg, nursing home) or a subject admitted with pneumonia following a recent hospitalization (overnight admission within 90 days prior to current admission).
- Has a known history of having experienced unstable cardiac disease (eg, unstable angina, myocardial infarction, acute congestive heart failure, unstable cardiac arrhythmia) within the 3 months prior to Screening or presents with a tachyarrhythmia (excluding sinus tachycardia).
- Has a QT interval corrected for heart rate using Fridericia's formula (QTcF) > 450 msec (males) or > 470 msec (females), are known to have long QT syndrome, use drugs of potential proarrhythmic or QT prolonging effect.
- 8. Has other contraindications to receiving a systemic fluoroquinolone antibiotic, including confirmed or suspected peripheral neuropathy, tendon disorder, myasthenia gravis, cirrhosis, aortic aneurysm, or central nervous system (CNS) disorder that may predispose to seizures or lower the seizure threshold.

- History or evidence of severe renal disease or has a calculated creatinine clearance (CrCl) of < 30 mL/minute, using the Cockcroft-Gault equation (Appendix 2). Requires any form of dialysis (eg, hemodialysis, peritoneal dialysis).

- 10. Significant immunological disease determined by any of the following:
  - Current or anticipated neutropenia defined as < 500 neutrophils/mm3
  - Known infection with Human Immunodeficiency Virus (HIV) and a cluster of differentiation 4 (CD4) count that is unknown or documented to be < 200 cells/mm^3 within the last year, or an Acquired Immune Deficiency Syndrome (AIDS)-defining illness
- 11. The receipt of cancer chemotherapy, radiotherapy, or potent, non-corticosteroid immunosuppressant drugs (eg, cyclosporine, azathioprine, tacrolimus, immune- modulating monoclonal antibody therapy, etc) within the past 3 months, or the receipt of corticosteroids equivalent to or greater than 40 mg of prednisone per day or for more than 14 days in the prior 30 days (Appendix 2). Exception: Systemic corticosteroids administered within 24 hours of randomization or any time after randomization as adjunctive therapy for the current episode of CABP (at any dosage) is allowed.
- 12. Requires acute pharmacologic intervention to stabilize blood pressure (BP) and/or adequate tissue perfusion OR meets septic shock criteria (meets ALL of the following):
  - Meets at least 2 criteria for sepsis as defined by the quick Sequential Organ Failure Assessment (qSOFA) score: (a) Altered mental status with Glasgow Coma Scale (GCS)
     < 15, (b) RR ≥ 22 breaths per minute, and (c) SBP ≤ 100 mmHg

  - Despite adequate fluid resuscitation, persistent hypotension requiring vasopressors to maintain mean arterial pressure (MAP) ≥ 65 mmHg
  - Serum lactate ≥ 2 mmol/L (serum lactate measurement is not required at Screening if any of the above septic shock criteria are not met)
- 13. PORT Risk Class I, II, and V patients.
- 14. Requires or expected to require Intensive Care Unit (ICU) admittance or invasive or noninvasive ventilation.
- 15. Known or suspected primary or metastatic neoplastic lung disease, aspiration pneumonia, active tuberculosis, cystic fibrosis, bronchiectasis, bronchial obstruction (eg, post-obstructive pneumonia), chronic neurological disorder preventing clearance of pulmonary secretions, or severe chronic obstructive pulmonary disease (COPD) (severe COPD is defined as known forced expiratory volume in 1 second [FEV1] < 50% of predicted in a patient with FEV1/forced vital capacity [FVC] < 70%; note that spirometry or pulmonary function testing is not required during Screening).

- 16. Pregnant or nursing (breastfeeding) women.
- 17. Has a history of hypersensitivity or allergic reaction (eg, anaphylaxis, urticaria, other significant reaction) to any tetracycline (eg, minocycline, doxycycline or tigecycline), to any fluoroquinolone or any of the components of the investigational product or comparator.
- 18. Has a history of pseudotumor cerebri, or prior (within 2 weeks prior to Screening) or planned concomitant use of isotretinoin.
- 19. Has a history of systemic lupus erythematosus or lupus-like syndrome.

- 20. History of lactose intolerance, lactase deficiency, or glucose-galactose malabsorption.
- 21. Has current evidence of pancreatitis.
- 22. Use of other investigational drugs within 5 half-lives or 30 days prior to Screening, whichever is longer.
- 23. Has previously been treated with omadacycline or previously enrolled in this study.
- 24. Any planned medical intervention that might interfere with the ability to comply with the study requirements.
- 25. Has a life expectancy of less than or equal to 3 months or any concomitant condition that, in the opinion of the investigator, is likely to interfere with evaluation of the response of the infection under study, determination of AEs, or completion of the expected course of treatment.

#### 6.4 Screen Failures

Subjects who sign the ICF but withdraw or are withdrawn from the study before random assignment to double-blind treatment are defined as screen failures. All screen failures should be recorded on the subject master list. Limited information including reason for screen failure will be recorded on the eCRF or interactive voice/web response system (IxRS) system for screen failures. Screen failure subjects may be re-screened at the discretion of the investigator and in consultation with the medical monitor as needed. Any subject who discontinues participation or is withdrawn before receiving a treatment assignment, and who is re-screened at a later time will be assigned a new subject number and recorded as re-screened.

# 7 STUDY TREATMENT(S)

## 7.1 Treatments Administered

Test articles will be supplied by Paratek Pharmaceuticals, Inc. (the sponsor). Test articles will be labeled according to regulations.

The test articles should be administered only to subjects who have provided informed consent and who meet all of the inclusion criteria and none of the exclusion criteria. Once the test article has been assigned to a subject, it must not be reassigned to another subject.

Following a Screening period of up to 24 hours, eligible subjects will be randomly assigned a dosing regimen of omadacycline or moxifloxacin. Intravenous treatment will be double-blind and oral treatment will be double-blind and double-dummy.

## 7.2 Identity of the Investigational Product: Omadacycline

Name	Omadacycline
Administration	Please reference Section 7.6

#### **Intravenous Formulation (Omadacycline)**

### **Oral Formulation (Omadacycline)**

Name	Omadacycline , 150 mg			

Preparation and	No special requirements
handling	
Administration	Please reference Section 7.6

## 7.3 Comparator Test Article: Moxifloxacin

#### Intravenous Formulation (Moxifloxacin)

Name	Moxifloxacin
Excipients	Sodium chloride, USP, glycine, Water for Injection, USP, disodium edetate, and hydrochloric acid for pH adjustment.
How supplied	Single-use ready-to use 250 mL flexibags as a sterile, preservative free, 0.8% sodium chloride solution of moxifloxacin hydrochloride (equivalent to 400 mg moxifloxacin).
Storage	Store at 25°C (77°F). Excursions permitted to 15°C to 30°C (59°F to 86°F). Do not store below 15°C (59°F).
Preparation and handling	No special requirements Please refer to Pharmacy Manual for additional information.
Administration	Please reference Section 7.6

### **Oral Formulation (Moxifloxacin)**

Name	Moxifloxacin Tablet, 400 mg
Excipients	Microcrystalline cellulose, mannitol, silica colloidal anhydrous, sodium starch glycolate, hydroxypropyl cellulose, talc, magnesium stearate, and film coat (polyvinyl alcohol, titanium dioxide, macrogol, iron oxide yellow, iron oxide red, and talc). Tablet is over-encapsulated with a Size 000 Swedish Orange hard gelatin capsule (red iron oxide and titanium dioxide).
How supplied	High-Density Polyethylene (HDPE) bottles with induction seal, child resistant closure and desiccant
Storage	Store at 25°C (77°F). Excursions permitted to 15°C to 30°C (59°F to 86°F)
Preparation and handling	No special requirements
Administration	Please reference Section 7.6

## 7.4 Dose Selection Rationale

The dosing regimen of omadacycline selected for this study is based on the nonclinical and clinical experience to date, including in vitro antibacterial activity, PK characteristics, clinical efficacy in prior studies, the overall safety and tolerability profile, and the FDA approved dosing regimen for CABP.

Either a regimen of 200 mg iv omadacycline once daily or 100 mg iv omadacycline every 12 hours (q12h) on Day 1 followed by 100 mg iv omadacycline administered once daily OR 300 mg po omadacycline once daily has been approved by US FDA for the treatment of adult patients with CABP caused by susceptible microorganism. The FDA-approved treatment duration for omadacycline is 7 to 14 days total.

The duration for the iv to po regimen in this study will be 7 to 10 days, with up to 14 days allowed for subjects with bacteremia at the Screening visit. The shorter regimen is supported by the efficacy observed in the previously completed CABP Phase 3 study, PTK0796-CABP-1200 where by Day 7 of treatment, > 80% of patients in the omadacycline treatment group had symptom improvement (as defined by the Early Clinical Response [ECR] endpoint) and had reached clinical stability.

### 7.5 Description of Treatments

		Study Day	Study Day	Study Days
Group	Test Article	1	2	3 to 10 a
1	Omadacycline	200 mg iv QD or 100 mg iv BID	100 mg iv	100 mg iv or 300 mg po
2	Moxifloxacin	400 mg iv	400 mg iv	400 mg iv or 400 mg po

Subjects will be randomized to 1 of the following treatment groups:

BID = twice a day dosing, iv = intravenous, po = per oral, PORT = pneumonia patient outcomes research team, QD = once a day dosing.

a The total duration of treatment for subjects is 7-10 days, with up to 14 days of treatment for subjects with bacteremia identified at Screening.

## 7.6 Test Article Administration

### 7.6.1 Intravenous Treatment Phase

The iv-treatment phase (minimum 2 days) will follow a double-blind, double-dummy design for omadacycline and moxifloxacin. Infusions of 100 mg omadacycline or matched placebo will be administered continuously, without interruptions, over 30 minutes ( $\pm$  5 minutes). On Day 1, if QD dosing is selected, the 200 mg infusion of omadacycline or matched placebo will be administered continuously, without interruptions, over 60 minutes ( $\pm$  5 minutes). On Day 1 of iv treatment, if twice a day dosing (BID) was selected, subjects on the moxifloxacin treatment arm will receive an additional placebo infusion to match the t = 12 h infusion. Infusions of moxifloxacin or matched placebo will be administered continuously, without interruptions, over 60 minutes ( $\pm$  5 minutes).

The first dose of test article should be administered within 4 hours of randomization. All infusion start and stop times are to be recorded in the source documents and on the eCRF. Because the color of the test article and placebo infusions are different, all infusion bags and iv tubing will be covered with materials provided by the sponsor (as described in the Pharmacy Manual) so that

subjects and blinded study personnel will not know the identity of the test article being administered. Subjects in each study arm will receive the same infusion volumes with the same blinded administration instructions. All iv infusions will be administered by qualified blinded personnel. However, unblinded personnel may administer the iv infusions provided they will not be performing any efficacy assessments. If gravity administration is not the standard of care, then an infusion pump may be used. If an infusion pump is used, then an unblinded administrator will be required. Subjects may receive iv treatment in certain outpatient centers in circumstances where the principal site investigator has identified that sufficient resources are available to complete all study procedures as defined in the protocol and the sponsor or sponsor's designee has reviewed and approved the process for outpatient iv test article administration.

Please refer to Table 1 for more detail on the Treatment regimens for iv dosing.

Infusion Timepoint a	Infusion Number	Omadacycline Arm b,c	Moxifloxacin Arm b,c
	1	omadacycline 100 mg in 100 mL NS	100 mL NS placebo
	2	250 mL NS placebo	moxifloxacin 400 mg in 250 mL 0.8% saline
t = 0 h		OR	
	1	omadacycline 200 mg in 100 mL NS	
	2	250 mL NS placebo	
t = 12 h (Only for BID dosing Day 1)	1	omadacycline 100 mg in 100 mL NS	100 mL NS placebo
t = 24 h	1	omadacycline 100 mg in 100 mL NS	100 mL NS placebo
	2	250 mL NS placebo	moxifloxacin 400 mg in 250 mL 0.8% saline
t = 48 h, then	1	omadacycline 100 mg in 100 mL NS	100 mL NS placebo
q24n	2	250 mL NS placebo	moxifloxacin 400 mg in 250 mL 0.8% saline

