## 7.10 Blinding

The investigator and sponsor will be blinded to treatment arm assignments in both the iv and po phases of the study.

The sponsor designee (eg, study statistical team, IxRS vendor, etc) will have a designated randomization administrator who will maintain the randomization codes in accordance with standard operating procedures to ensure the blind is properly maintained, and that only sponsor personnel who require knowledge of treatment assignments will be unblinded (eg, staff involved in maintaining the randomization codes).

Because the color of the iv test article infusions and placebo infusions differ, all infusion bags and iv tubing will be covered with materials provided by the sponsor so that subjects and blinded
study personnel will not know the identity of the test article being administered. The infusion regimen will follow a blinded design with subjects in each study arm receiving the same infusion volumes with the same administration instructions. Blinded study personnel will administer the infusions and collect, review and enter data regarding the iv infusions (eg, start and stop times) into an eCRF. If gravity administration is not the standard of care, then an infusion pump may be used. If an infusion pump is used, then an unblinded administrator will be required. Personnel identified as unblinded administrators will not participate in any study procedures other than iv administration of test article and the collection, review and entry of iv related data (eg, start and stop times) into an eCRF.

During the po phase, a double-blind, double-dummy design will be used to ensure the blind is maintained. Subjects in the omadacycline arm will receive active omadacycline tablets and matched comparator over-encapsulated placebo tablets. Subjects on the moxifloxacin arm will receive omadacycline placebo tablets and active over-encapsulated moxifloxacin tablets.

The unblinded source documentation binder containing all descriptions of pharmacy preparations and infusions or distributions of test article and any unblinded subject randomization data should be stored separately, and under lock and key, separate from the documents containing blinded information.

Data that could potentially lead to unblinding will not be accessible to anyone other than the following site personnel:

- unblinded study pharmacist or designee
- unblinded study monitor
- unblinded administrator(s)

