6.1.4.4 Test Article Therapy

Subjects must meet all of the following to be included in the CE populations:

- Received at least 1 dose of active test article and the correct test article based on the randomization assignment.
- Study personnel involved in the assessment of efficacy remained blinded to study treatment, unless a treatment limiting adverse event (AE) occurred which required emergency unblinding.
- Evaluable failure: The subject received the first 2 doses (if receiving 200 mg iv QD on Day 1) or 3 doses (if receiving 100 mg iv on Day 1) of active test article (omadacycline group) or first 2 doses of active test article (moxifloxacin group) and the investigator classifies the subject as a Clinical Failure at the EOT Visit (CE-EOT population) or the overall Clinical Response (based on the investigator's assessment) at the PTE Visit (CE-PTE population) is Clinical Failure.
- Evaluable success: The subject received the first 3 doses (if receiving 200 mg iv QD on Day 1) or 4 doses (if receiving 100 mg iv on Day 1) of active test article (omadacycline group) or the first 3 doses of active test article (moxifloxacin group) and the investigator classifies the subject as a Clinical Success at the EOT Visit (CE-EOT population) or the overall Clinical Response (based on the investigator's assessment) at the PTE Visit (CE-PTE population) is Clinical Success.

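### Protocol 7.6.1 and 7.10 set different limits on unblinded infusion staff; under 7.6.1 alone, staff who know the arm could record AEs and take peri-infusion vital signs

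*Protocol*

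**What the plan says.** Both sections start from the same default. Protocol 7.6.1 states "All iv infusions will be administered by qualified blinded personnel", and 7.10 states "Blinded study personnel will administer the infusions and collect, review and enter data regarding the iv infusions". Both also say that a pump makes an unblinded administrator necessary (7.10: "If an infusion pump is used, then an unblinded administrator will be required").

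They differ on the exception. Protocol 7.6.1 adds that "unblinded personnel may administer the iv infusions provided they will not be performing any efficacy assessments". This sentence comes before the pump sentences and does not depend on them. Protocol 7.10 has no such general permission. After its pump sentence it says "Personnel identified as unblinded administrators will not participate in any study procedures other than iv administration of test article", apart from collecting, reviewing and entering iv-related data.

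Section 7.10 also fixes the position of the decision-maker: "The investigator and sponsor will be blinded to treatment arm assignments in both the iv and po phases of the study". In the SAP, the only blinding condition on staff is an inclusion criterion for the clinically evaluable populations (6.1.4.4): "Study personnel involved in the assessment of efficacy remained blinded to study treatment", with an exception for emergency unblinding after a treatment-limiting adverse event.

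**The concern.** The same people are under two rules of different width. Section 7.6.1 is where the protocol describes how infusions are given, and its proviso does not refer to 7.10. A site that staffs the iv phase from that sentence could conclude that an unblinded nurse may do any study task that is not an efficacy assessment.

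What is at stake is the blinding of part of the safety data. Evaluating safety is a secondary objective (Protocol 4.2). Adverse-event elicitation is open to influence by the person asking, since Protocol 8.21 relies on a nonspecific question to the subject as one source of reports. The peri-infusion blood pressure and heart rate readings are summarised by time point in SAP 10.2. If staff who know the arm collect either, the double-blind description no longer holds fully for those data.

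**Working it through.** The point turns on the text, and there is no figure to reproduce. The steps are to compare the two rules, then ask for each task whether another passage already reserves it for a blinded person.

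**Step 1: the two rules.**

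| | Protocol 7.6.1 | Protocol 7.10 |
|---|---|---|
| Default infuser | Blinded | Blinded |
| When an unblinded infuser is provided for | In general, and necessarily with a pump | With a pump only |
| What that person may not do | Efficacy assessments | Any study procedure except iv administration and iv-related data work |

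Anyone who obeys the 7.10 limit performs no efficacy assessments and so obeys 7.6.1. Someone who obeys only 7.6.1 can breach 7.10, either by doing a non-efficacy procedure or by infusing unblinded without a pump. The rules are therefore nested, and one is wider than the other in both scope and trigger.

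**Step 2: which tasks the wider rule leaves open.** Setting 7.10's limit on unblinded administrators aside:

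- *Continue, switch or stop decisions* belong to the investigator (7.6.3, 7.6.4, 7.6.5, 7.6.6.1), who is blinded. Blinded site staff transfer the daily decisions to the eCRF (7.6.3 for iv, 7.6.6.1 for oral). Section 7.6.5 omits the word *blinded* for the transfer of the switch information. **Closed, apart from that omission.**
- *Causality* is assessed by the investigator (8.21.2). **Closed.**
- *Early Clinical Response* is computed by program from the investigator's symptom ratings (8.13.1.1). *Response at EOT and PTE* is the investigator's assessment (8.13.1.2, 8.13.1.3). These are efficacy assessments, so 7.6.1 bars unblinded infusers from them too. **Closed.**
- *Clinical Stability* sits under Efficacy Assessments (8.13.2) and derives from the investigator's assessment of vital signs. On a natural reading the 7.6.1 proviso already covers it. **Closed on that reading.**
- *Adverse-event elicitation and recording*: 8.21 names neither who asks the question nor who writes down the answer, and sets no blinding condition. **Open.**
- *Blood pressure and heart rate* within 30 minutes before, and about 1 hour after, the Day 1 and Day 2 infusions: 8.5 names no assessor. A person giving the infusion could plausibly take them. **Open.**

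**Step 3: how many subjects.** Every subject is due at least 2 days of iv treatment (7.6.1, 7.6.5), so the iv phase concerns the whole trial of about 670 planned subjects. Neither document gives the frequency of pump use or of unblinded infusion without a pump. The affected number could lie anywhere from none to all of those dosed.

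**Step 4: what happens after a breach.** Infusion staff who go beyond 7.10 commit a protocol deviation. Protocol 13.6.1 permits no authorised deviations and reports significant ones in the study report. SAP 12.1 lists all deviations and has the sponsor class them as major or minor before unblinding. Its example categories do not name a blinding breach, but the list is open-ended.

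**The case against.** The strongest reply is that this is not a contradiction. Section 7.6.1 states one necessary condition, and 7.10, the section devoted to blinding, adds a stricter one. Sites are bound by the whole protocol, and nothing in 7.6.1 positively authorises unblinded staff to collect adverse events. Pump cases are also the best protected, because in 7.10 the restriction directly follows the pump sentence. The Pharmacy Manual, which is not among the documents, may settle the matter.

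Much of this stands. A site that reads both sections and applies the stricter one has no problem, and the permission to do other tasks is inferred from 7.6.1 naming only one bar. The reply does not remove the difference in trigger: 7.6.1 allows an unblinded infuser without a pump and 7.10 does not provide for one. Nor does it explain why the administration section should carry a looser rule than the blinding section.

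A reader might also infer that 7.6.1 lets people who know the arm judge causality or make switch and stop decisions, and through rescue treatment affect clinical failure. The documents do not support that. Those judgements are the investigator's, and the investigator is blinded. At most, information gathered by unblinded staff could reach a blinded decision-maker.

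A further inference is that SAP 6.1.4.4, being limited to efficacy assessors, would let breaches of 7.10 pass unnoticed. That criterion only decides membership of the clinically evaluable populations. It is not the trial's check on blinding; deviation handling is.

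**Conclusion.** The discrepancy is real and worth correcting, but its reach is narrow. Protocol 7.6.1 and 7.10 differ on what unblinded infusion staff may do and on when they may be used. The exposure is adverse-event elicitation and recording, plus peri-infusion blood pressure and heart rate on Days 1 and 2, and it arises only where a site works from the 7.6.1 proviso without applying 7.10. Its size cannot be derived, and the documents do not support calling it either common or rare.

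The SAP's primary analysis, Early Clinical Response in the ITT population, is not opened by this difference, because both sections keep unblinded infusers away from efficacy assessments. This conclusion assumes that the investigator stays blinded as 7.10 requires, and that vital signs used for Clinical Stability count as an efficacy assessment, as their place in Protocol 8.13 suggests.

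**What to change.** 1. In Protocol 7.6.1, replace the proviso with the 7.10 limit, so that unblinded administrators "will not participate in any study procedures other than iv administration of test article" and the associated collection, review and entry of iv data.
2. Make 7.6.1 and 7.10 agree on whether an unblinded person may infuse when no pump is used.
3. In Protocol 7.6.5, specify that the site staff who transfer the switch information to the eCRF are blinded, as 7.6.3 and 7.6.6.1 already do for the daily decisions.
4. Leave SAP 6.1.4.4 unchanged. Widening it to safety assessors would remove subjects from an efficacy population because of who recorded an adverse event. It would protect no safety result, since safety is analysed in the Safety population (SAP 6.1.2, section 10). Name blinding breaches as a deviation category in SAP 12.1 instead.

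The cost is a few words in two protocol sections, possibly a sentence in 7.10, and one added category in the SAP. The limit itself needs no extra staff, because 7.10 already requires the separation.
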